The aim of the study is to conduct an RCT comparing optimised MDI therapy (using rapid and twice daily long-acting insulin analogues) with CSII in adult type-1 diabetic patients provided with high quality structured education (Dose Adjustment for Normal Eating-DAFNE).

- 1) During the RCT the following measures will be assessed over 2 years:
 - a) biomedical outcomes (HbA1c, rates of hypoglycaemia, insulin dose, body weight, albumin-creatinine ratio),

b) quantitative and qualitative psychosocial outcomes (quality of life (generic and diabetes specific), treatment satisfaction, fear of hypoglycaemia, hypoglycaemia unawareness, self-efficacy, social support, adherence to treatment, emotional well-being, acceptability of technology),

c) adverse events (severe hypoglycaemia. hospital admissions with hypoglycaemia, diabetic ketoacidosis)

[figure not shown]
2) Through a combined analysis of the quantitative and qualitative measures we will identify factors which predict and/or help explain outcomes on CSII.

3) A cost effectiveness analysis will be undertaken to determine whether the marginal benefits of CSII over optimised MDI (if demonstrated) are commensurate with the marginal costs, as reflected in a cost per QALY acceptable to NICE.

3. Trial Design

REPOSE is a multi-centre parallel group, cluster randomised controlled trial, in which 280 adults with type-1 diabetes will be recruited from 7 trusts/Health Boards across the UK. The participants will be male or female above the age of 18 yrs. The participants will be allocated a place on a week-long DAFNE course depending on their availability. Prior to the course starting, the courses will be randomly allocated to be either CSII or MDI treatment. Participants will be requested to attend visits in order to obtain biochemical, psychosocial and health economic follow-up measures at baseline (i.e. after course allocation), 6 months, 1 year and 2 years after they have completed the DAFNE course. The diagram below gives an overview of the trial design.

Figure 1. Model of Trial Design

Primary Endpoints

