Once the participants have been randomised and are attending the baseline data collection visit, all participants will be asked whether they would like to be contacted by a qualitative researcher to be invited to participate in the qualitative psychosocial element of the trial. From this, a representative sub-sample of around 40 participants, to include 20 from the CSII arm and 20 from the MDI arm of the trial, will be recruited into the qualitative arm of the study. These patients will be interviewed within 2 weeks of completion of their courses and around 6 months later. Patients' educators will also be invited to take part in an interview and these interviews will also take place within about 2 weeks of the course completion.

Data collection has been timed to coincide for the quantitative and qualitative elements at 6 months post DAFNE course. Both teams will work closely together to share ideas and findings and the qualitative work can therefore be used to help in the interpretation of findings arising from the quantitative analysis.

Figure 2. Model of Qualitative Study Design

Secondary Endpoints/Outcome measures

Participant post course interviews

Participants will be interviewed regarding:

a) Understandings of the trial and motivation for participation.

b) Views about outcome of randomisation.

c) Expectations/concerns about trial participation and (if relevant) change to CSII. d)

Experience of/views about the course and (if relevant) change to CSII.

e) Changes they have made to diabetes management since the course and short/long terms goals set.

f) Likes/dislikes of CSII or MDI treatment.

Educator post-course interviews

Educators will be interviewed regarding:

a) Insight and experience of what took place on the course.

b) Recommendations for future course development.

c) Recommendations for support that should be offered to patients who move onto pumps.

Participant 6 month follow-up interviews

Participants will be interviewed regarding:

a) Barriers and facilitators to sustaining diabetes management.

b) Reasons for CSII discontinuation and/or treatment non-adherence.

c) Changing perceptions of their disease.

d) Patients views and recommendations regarding support received both prior and subsequent to the course.

Health Economic Evaluation

Introduction

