After consent, participants will be allocated to courses depending on their availability in relation to the dates of the courses. A computerised system will be used within Sheffield Clinical Trials Unit in order to randomise 48 DAFNE courses to either MDI or CSII courses across the 8 participating sites. The randomisation for courses will be stratified by site. Within each centre the first four courses will be randomised in pairs (one MDI, one CSII). The remaining courses will be randomised by minimisation. PIs/Educators will attempt to have allocated 7 individuals to each course at least six weeks prior to the course commencing. By this time, the CTRU will inform the centre whether the course has been allocated as a CSII course or as an MDI course and confirm the allocation of a course number. The PIs and educators will have been blinded to the type of course being delivered until four to six weeks before the course commences and staff within the trials unit will be blinded to the identity of those participating. The participant will find out which course they are allocated to four weeks prior to the DAFNE course. Once the course number has been allocated to the course and the type of course is known to the site, further participants will only be allocated to the course in the situation described below.

If for any reason participants are unable to take part in the course at short notice, they will only be able to participate in the same arm of the study as the course they were originally allocated to. The patient will be given possible dates for the next relevant course and will be informed when that course is due to commence as soon as the PI/educator finds out.

In order to maximise recruitment for the courses, the PI's and educators will be able to invite a new participant to take the place of somebody unable at attend. This will occur only where there is a list of reserve participants in place, prior to the time when the course allocation has been revealed to the educators. In this case, the next person on that list would be invited to participate in that arm of the study. The patient will be allocated a screening number at the point at which they have been invited to participate and have had the inclusion/exclusion criteria check. This screening number will be used to assess the next person on the list.

7. Trial Treatment

Insulin

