The 5-day structure of the adult DAFNE course and additional follow-up sessions have been maintained while modifying the course to incorporate the additional skills and learning outcomes of CSII therapy. Thus the principles of insulin dose adjustment taught on the adult course are maintained. The additional components of the course have been modelled informally during existing CSII courses in the participating centres and in a pilot study which has been run in 3 centres. The need to introduce CSII skills requires the addition of a pre-course session, which will be run approximately 2 weeks before the DAFNE course. It is important that any skills for use of CSII are taught entirely separately from the course principles since we need to ensure that CSII participants do not get any extra tuition compared to the MDI participants in order to minimise bias. The participant will learn to use the pump on saline from the point of the pre-course session for CSII skills, and will be asked to switch to insulin on the evening before the DAFNE course. Clinical care would continue for patients as normal after the course. Participants will also be given contact details of the educators, as they would for a standard DAFNE course, in case they wanted to contact a clinician for advice on an ad hoc basis.

Minimisation of Bias

In addition to both courses being run over equal time span, bias will be minimised through:

- 1. Ensuring that participants in both arms of the study have a bolus calculator to work out the amount of insulin they should be taking.
- 2. Participants in both arms of the study recording insulin usage/dose through use of a recall question rather than recording directly. This is because a pump would automatically record insulin used, meaning that measurements across the arms are likely to be different methods if we asked participants to record the actual measures.
- 3. Fidelity testing to ensure that the principles of insulin adjustment are delivered in a similar fashion for both CSII and MDI courses.

Fidelity Testing

Fidelity testing will be carried out to ensure that the courses are delivered according to DAFNE philosophy and principles and that the educators delivering the courses have

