the skills to deliver these principles. Since there is already a robust system being used for quality assurance of the MDI courses and these will have already been audited, it is only the CSII courses that will need to be audited in order to check that they run to the same standard.

An experienced DAFNE educator from one of the participating trusts will be employed as an auditor. The auditor will visit each site to observe one of the courses on a Wednesday. Wednesday has been chosen since both the nutrition and diabetes expert that teach on the course will deliver parts of the course on that day. Patients on the course should have settled into the course and be more relaxed by the 3rd day. The auditor will assess that the staff are appropriately trained within the trust and the session delivery. This will be completed through assessment of whether the correct DAFNE content is delivered, whether it is delivered in the correct order and whether the best methods of delivery are used. The educator will be assessed according to certain criterion in a peer support core skills form.

[figure not shown]
Once the auditor has completed the assessment, feedback will be given in order that the trust and the educators may resolve any problems and the assessment sheets will be kept on file so that any differences in course delivery between the arms of the study may later be identified.

8. Assessments and procedures

Data Collection Procedure

Once participants have been enrolled and allocated a course date, the data collection process starts. Data collection occurs at baseline, course, 6 month, 1 year and 2 year visits. The process includes a post course and 6 month interview for those participants who have consented to and been selected for the qualitative psychosocial element of the study. The participants will be sent data collection documents to fill out approximately 2-6 weeks before the 6 month, 1 year and 2 year visits and are given reminder letters, phone calls or texts prior to the visit. This is so that the patients may bring the completed forms with them to the visit thereby maximizing the return of data. CRFs are filled out by the educator in an interview style at the visit.

Figure 5 and table 1 below outline the data collection process, instruments collected and outcomes of the study covered.

[figure not shown]

Table 1. Documents for Data Collection

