Time Period of Study	Collection Tool	When Sent/Given to Patient	When Collected	Who Collects	Which Element(s) of the Trial Relevant for	What Outcome is Covered
Recruitment	Screening Questionnaire	At time of recruitment conversation (phone or face- to-face)	At time of recruitment conversation (phone or face- to-face)	PIs/Educators approaching patients for recruitment	All	If there are problems with recruitment we can understand why and try to rectify
Recruitment	Inclusion/Exclusion Checklist	At time of recruitment conversation (phone or face- to-face)	At time of recruitment conversation (phone or face- to-face)	Pls/Educators approaching patients for recruitment	All	To ensure correct protocol deviations and violations are avoided
Recruitment	Invitation letter/email with screening & Patient Information Sheet	Sent out at time of recruitment	Returned by participant if willing	PIs/Educators approaching patients for recruitment	All	If there are problems with recruitment we can understand why and try to rectify
Baseline	Informed Consent Sheet - includes full participant contact details	See informed consent process diagram	See informed consent process diagram	Pls/Educators	All	To ensure all participants have consented appropriately
Baseline	Trial CRF	Baseline Visit	Baseline Visit	Educators	Biomedical measures	HbA1c, body weight, lipids & proteinuria, diabetic ketoacidosis, severe hypoglycaemic episodes
Baseline	Baseline Hypo Recall Log	Baseline Visit	Baseline Visit & Course Visit	Educators	Biomedical measures	12 months severe hypo recall & 4 weeks moderate hypo recall
Baseline	Instructions for recording hypos	Baseline Visit	Not collected	Educators	Biomedical Measures	Severe and moderate hypoglycaemic episodes

Time Period of Study	Collection Tool	When Sent/Given to Patient	When Collected	Who Collects	Which Element(s) of the Trial Relevant for	What Outcome is Covered
Baseline	Blood and urine samples	Baseline visit	Baseline visit	Laboratory	Biomedical measures	HbA1c, lipids & proteinuria, albumin-creatinine ratio
Baseline	Demographic questionnaire – (in baseline psychosocial pack)	Baseline visit	Course Visit	Educators	Quantitative psychosocial	Demographics
Baseline	WHOQOL-BREF (in psychosocial questionnaire pack)	Baseline visit	Course Visit	Educators	Quantitative psychosocial	Generic quality of life
Baseline	DSQOL (in psychosocial questionnaire pack)	Baseline visit	Course Visit	Educators	Quantitative psychosocial	Diabetes specific quality of life

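### Baseline questionnaires are collected only at the course, so some may be completed after participants know their arm and, in the CSII arm, after pump wear has begun

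*Protocol*

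**What the plan says.** - **When baseline happens.** Section 3 (Trial Design) takes measures "at baseline (i.e. after course allocation"). Section 4 (Qualitative Component, Study Design) describes the visit with the words "Once the participants have been randomised and are attending the baseline data collection visit". Section 8 (Data Collection Procedure) is looser: "Once participants have been enrolled and allocated a course date, the data collection process starts".
- **When the arm is known.** Section 6 (Randomisation) keeps PIs and educators "blinded to the type of course being delivered until four to six weeks before the course commences". For participants it says: "The participant will find out which course they are allocated to four weeks prior to the DAFNE course".
- **What happens next in one arm only.** Section 7, DAFNE Course (Pump), adds a pre-course session "which will be run approximately 2 weeks before the DAFNE course". It continues: "The participant will learn to use the pump on saline from the point of the pre-course session for CSII skills". The change to insulin in the pump comes the evening before the course.
- **How the questionnaires are handled.** In section 8, Table 1, the row for "DSQOL (in psychosocial questionnaire pack") shows hand-out at the baseline visit and collection at the course visit, by educators. The rows for WHOQOL-BREF, EQ-5D, SF-12, HFS, DTSQ and HADS follow the same pattern. The baseline hypoglycaemia recall log is given at the baseline visit and collected at both the baseline and the course visit.

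**The concern.** A baseline is useful because allocation cannot have influenced it. These scales are self-reported and the trial is open. A participant who fills in the pack in the last weeks before the course already knows the arm. A CSII participant may also be wearing the device while still injecting insulin. Answers on treatment satisfaction, fear of hypoglycaemia, mood or quality of life given at that point may no longer describe the state before allocation, and the effect need not be the same in the two arms.

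What is at stake is the comparison of psychosocial outcomes between arms and over time, which section 4 sets as an aim, and the QALY estimate, because section 8 (Health Economic Data Collection and Analysis Procedures) builds QALYs from the area under the EQ-5D curve. The hypoglycaemia recall log raises a related question. It asks for four weeks of moderate episodes. If that part is completed at the course, the recall period coincides with the four weeks of known allocation, and the educators who collect it also know the arm. Table 1 does not say which part is collected when.

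**Working it through.** The Protocol gives no figure on this point to reproduce, and the sample size in section 9 is unaffected. The check is a timeline followed by an illustration of size.

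**1. Timeline (weeks relative to the course, from sections 6 to 8)**

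| Week | Event | Arm |
|---|---|---|
| −6 to −4 | Educators learn the arm | both |
| −4 | Participants learn their arm | both |
| about −2 | Pre-course session; pump on saline from here | CSII only |
| evening before | Pump switched to insulin | CSII only |
| 0 | Baseline pack collected | both |

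Collection therefore falls 0 − (−4) = 4 weeks after disclosure and about 0 − (−2) = 2 weeks after pump wear starts. The date of the baseline visit relative to week −4 is not stated, so the pack may be handed out before or after disclosure. Either way, Table 1 leaves it with the participant until week 0.

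**2. Bias if disclosure shifts the baseline (assumed values, not in the Protocol)**

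Let s be the net shift in mean baseline score, CSII minus MDI, caused by knowing the arm or wearing the pump. It is averaged over all packs in each arm, so it shrinks in proportion to the share completed early. Let b be the slope of follow-up score on baseline.

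- Baseline-adjusted effect = (difference at follow-up) − b × (difference at baseline), so the bias is −b × s.
- Change score: b is replaced by 1, so the bias is −s.
- Follow-up means compared with no use of baseline: bias 0.

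Absolute bias in SD units:

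| b | s = 0.1 | s = 0.2 | s = 0.3 |
|---|---|---|---|
| 0.3 | 0.03 | 0.06 | 0.09 |
| 0.5 | 0.05 | 0.10 | 0.15 |
| 0.7 | 0.07 | 0.14 | 0.21 |
| 1 (change score) | 0.10 | 0.20 | 0.30 |

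The sign is not known. On a scale where higher is better, pleasure at getting a pump would raise the CSII baseline and understate its benefit. Worry about the device would do the reverse. MDI participants know their arm too, so only the net difference counts.

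**3. QALYs**

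The Protocol specifies an area under the curve but no interpolation rule. I assume a trapezoid over visits at 0, 0.5, 1 and 2 years. The weights are:

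- baseline: 0.5 × 0.5 = 0.25
- 6 months: 0.5 × (0.5 + 0.5) = 0.5
- 1 year: 0.5 × (0.5 + 1) = 0.75
- 2 years: 0.5 × 1 = 0.5

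These sum to 2. Baseline EQ-5D carries 0.25 / 2 = 12.5% of the total, so a shift of d in mean baseline EQ-5D moves the unadjusted two-year QALY difference by 0.25 × d.

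**The case against.** The case on the other side has five parts.

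- **Table 1 fixes hand-out and collection, not completion.** Many participants may fill in the pack on the day they receive it. This stands: the Protocol permits late completion but does not show that it occurs. The flow diagrams, including Figure 5 on data collection, were not available in the text reviewed and might specify an order, so I do not say that the plan lacks one.
- **The wording in section 3 may be innocent.** Sections 3 and 6 both speak of giving participants a place on a course by availability, separately from randomising the course, and section 8 refers only to a course date. Course allocation can therefore mean a place rather than an arm. Section 4 does say randomised, but being randomised is not the same as knowing the arm. This stands as an ambiguity, and it does not alter the collection rule in Table 1.
- **A reader might infer that baseline HbA1c, and hence the population at or above 7.5% and the primary covariate, is compromised.** The Protocol does not support that. HbA1c is sampled at the baseline visit and not at the course. It is measured in a central laboratory and, by section 3, reflects the previous 6 to 8 weeks. The pump holds only saline until the evening before the course.
- **The analysis may not use these baselines.** Section 9 (Quantitative Psychosocial Analysis) lists t-tests, ANOVA and possibly multiple regression, and names no baseline-adjusted model for these scales. A plain comparison at follow-up would carry no such bias. This stands, but change over time is a stated aim, and baseline EQ-5D enters the area under the curve whichever test is used.
- **A strict rule cannot be met by everyone.** Section 6 lets reserves step in after the arm is revealed and moves those who miss a course to a later one in the same, already known, arm. The August 2012 review counted 18 withdrawals before the course among 168 randomised (18 / 168 = 10.7%), so late replacement is not rare. This stands, and the fix has to allow for it.

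**Conclusion.** The point holds as a timing weakness in the self-reported baselines. Followed as written, Table 1 allows the psychosocial pack to be completed up to about four weeks after participants learn their arm and, in the CSII arm only, up to about two weeks into pump wear. Those baselines could then differ by arm as a result of allocation.

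How many packs are affected, and by how much, cannot be known from the Protocol. The working range of 0.03 to 0.21 SD for an adjusted effect and 0.1 to 0.3 SD for a change score rests wholly on the assumed shift and slope, and it applies only if the analysis uses baseline in one of those ways. The effect on QALYs is small, since baseline carries one eighth of the area under the assumed trapezoid. The finding concerns secondary and ancillary endpoints. It is not evidence that any baseline was in fact contaminated, and it does not reach the primary HbA1c analysis.

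**What to change.** - **Table 1:** have the baseline pack and the hypoglycaemia recall log completed and handed in at the baseline visit, with that visit held before the arm is disclosed to the participant wherever possible. Section 6 already aims to fill courses at least six weeks ahead and tells participants at four weeks, so most visits can be scheduled this way.
- **Completion date:** record one on every pack.
- **Exceptions:** flag late reserves, participants moved to a later course in a known arm, and any packs already dated after disclosure. Repeat the psychosocial and QALY analyses without them.
- **Section 3:** state that baseline follows the offer of a course place and precedes disclosure of the arm, and bring the wording in sections 4 and 8 into line.

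The cost is scheduling, a change to Table 1 and extra time at the visit for the questionnaires. No new visit, staff or instrument is needed. A minority of participants will still miss the timing, which is why the flag and the repeat analysis are part of the change.

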Hypoglycaemia is a major side effect of insulin treatment, which prevents many patients from achieving target glucose levels. CSII has been shown to reduce hypoglycaemia in some studies but since DAFNE and similar educational interventions are also associated with reduction in severe episodes we may have insufficient power to detect a difference in the rate of severe episodes between the two groups. During the last NICE appraisal of CSII, the question of the impact of moderate hypoglycaemia was raised. The point was made that moderate hypos, sufficient to interrupt activities of daily living, might because of greater frequency, have more cumulative effect on quality of life than severe hypos. Furthermore, moderate episodes are likely to be more frequent than severe events. We will therefore record both severe and moderate episodes of hypoglycaemia in participants. This should increase power and identify the ability of CSII to reduce rates of hypoglycaemia. It will also be possible to assess the effects of both, by comparing quality of life measures in those with only moderate hypos, versus those with moderate and severe.

Severe hypoglycaemia – any episode leading to cognitive impairment sufficient to cause either coma or requiring the assistance of another person to recover (27).

Moderate hypoglycaemia – any episodes which could be treated by that individual, but where hypoglycaemia caused significant interruption of current activity, such as having caused impaired performance or embarrassment or having been woken during nocturnal sleep.

Insulin dose

Some studies have indicated that CSII results in the use of less insulin. We will therefore record participants' self-reported insulin dose at each time point and calculate units/kg body weight.

Body Weight

If CSII treatment results in the use of less insulin, it may have a favourable effect on weight since with less insulin there is a propensity for the body to store fewer nutrients. We will therefore record weight at each time point of the trial.

Lipids and proteinuria

A recent study (26) reported little difference in HbA1c for CSII compared to MDI but found less progression to microalbuminuria in the CSII group, and also lower cholesterol and lower insulin dose.

Blood samples will be taken using local labs and lipids (including HDL cholesterol). Albumincreatinine ratio (a sensitive measure of proteinuria) will be measured from urine samples.

Diabetic-Ketoacidosis

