Post 6 Months, 1 year, 2 year	Post diary instructions	Sent out 4 weeks prior to 6 month, 1 year & 2 year visits	Not collected	Educators	Biomedical measures	Moderate hypoglycaemic episodes for next 4 week period
Post 6 Months, 1 year, 2 years	Post hypoglycaemia recall log	6 month, 1 year & 2 year visits	6 month, 1 year & 2 year visit	Educators – filled out in conjunction with diary	Biomedical measures.	Moderate hypoglycaemic episodes for preceding 4 week period
Post 6 Months, 1 year, 2 years	Blood and urine samples	6 month, 1 year & 2 year visits	6 month, 1 year & 2 year visit	Laboratory	Biomedical measures	HbA1c & lipids, proteinuria & albumin-creatinine ratio at 1 and 2 years but not 6 months
Post 6 Months, 1 year	Post Psychosocial questionnaire pack (see entries for baseline pack above for separate questionnaires included except for exclusion of baseline demographics and change to DTSQc questionnaire at 1 year)	Sent out approximately 2-6 weeks prior to 6 month & 1 year visits	6 month & 1 year visit	Educators	Quantitative psychosocial, health economics	See entries for baseline pack above for all outcomes covered

Time Period of Study	Collection Tool	When Sent/Given to Patient	When Collected	Who Collects	Which Element(s) of the Trial Relevant for	What Outcome is Covered
Post 2 years	Post Psychosocial questionnaire pack (see entries for baseline pack above for separate questionnaires included) except for the following changes: - Exclusion of baseline demographics - Inclusion of DAFNE principles, use of bolus calculators and use of pump features	Sent out approximately 2-6 weeks prior to 2 year visit	2 year visit	Educators	Quantitative psychosocial, health economics	All outcomes included in the psychosocial questionnaire pack with the addition of: - DAFNE principles - Use of bolus calculators - Use of pump features
Ongoing collection	Severe hypoglycaemia episodes log	Ongoing collection by telephone and CRFs at each visit	Ongoing collection by telephone and CRFs at each visit	Educators – filled out in conjunction with diary	Biomedical measures.	Severe hypoglycaemia episodes throughout duration of the trial
Ongoing collection	AE Identification log	Ongoing collection by telephone and CRFs at each visit	Ongoing collection by telephone and CRFs at each visit	Educators	Biomedical measures	Safety endpoints

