Linear models of insulin usage, body weight, lipids and proteinuria will also be analysed at 2 years with baseline measures as covariates. We will use Poisson regression (or a zero-inflated Poisson regression if necessary) on the number of hypoglycaemic episodes in 2 years, which should also have more power than an analysis based on dichotomy of having experienced/not experienced an episode. Again, GEE will be used for these analyses to account for clustering.

Subgroup Analyses

The analyses outlined above will also be completed for sub-groups stratified at baseline by participants with HbA1c level < and \geq 7.5% (58mmol/mol).

Primarily data will be analysed with missing data excluded. A secondary analysis will also be included using multiple imputation.

Quantitative Psychosocial Analysis

All variables will be subject to statistical analysis. Descriptive and inferential statistical analysis will be conducted using T-tests and ANOVA to compare means, crosstabs to explore individual variables, non-parametric tests including chi-square, correlational analysis and possibly multiple regression analysis. Statistical significance will be defined as $p \le 0.05$ with 95% confidence intervals.

Primarily data will be analysed with missing data excluded. Secondary analyses will also be completed with a) a mean score for each missing questionnaire and b) a minimum score for each missing questionnaire.

A full Statistical Analysis Plan will be submitted at a later date in order to detail this section of the protocol.

10. Trial Supervision

Three committees are being established to govern the conduct of the study:

- 1. Trial Management Group (TMG)
- Trial Steering Committee (TSC)
 Data Monitoring and Ethics Committee (DMEC)

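### Comparing quality of life in moderate-only against moderate-plus-severe participants cannot separate the contribution of moderate hypoglycaemia, although the protocol says it will assess both

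*Protocol*

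**What the plan says.** The Hypoglycaemia paragraph under Biomedical Endpoints (Protocol section 3) explains why moderate episodes are recorded. At the last NICE appraisal of CSII, "the question of the impact of moderate hypoglycaemia was raised", on the argument that such episodes "might because of greater frequency, have more cumulative effect on quality of life than severe hypos". The protocol then commits to recording both types, to increase power and to see whether CSII reduces rates. It adds that one can "assess the effects of both, by comparing quality of life measures in those with only moderate hypos, versus those with moderate and severe".

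Table 1 (section 8) gives the recording windows. The follow-up recall log covers "Moderate hypoglycaemic episodes for preceding 4 week period" at 6 months, 1 year and 2 years. The severe log covers "Severe hypoglycaemia episodes throughout duration of the trial".

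Section 9 (Quantitative Psychosocial Analysis) lists general methods, ending with "correlational analysis and possibly multiple regression analysis". Section 4 (Quantitative component, Study Design) mentions predictors and mediators of outcomes in general terms. Neither place ties a method to moderate hypoglycaemia.

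**The concern.** The question attributed to NICE is whether moderate episodes, through their number, weigh more on quality of life than severe ones. Answering it needs variation in moderate episodes: people with none, or people with few against people with many. The stated comparison offers neither by design, because having had moderate episodes is a condition of entry to both groups. What distinguishes the groups is severe episodes.

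The risk is misreading. A null result could be taken to mean that moderate episodes do not matter, and a positive one could be credited to both types. The protocol says the trial is meant to inform the next NICE reviews, so a comparison that is said to answer a NICE question should be able to do so.

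The groups are also formed by events after randomisation, so any difference is an association and not an effect.

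**Working it through.** The protocol gives no sample size, power or other figure for this comparison, so there is none to reproduce. The check is one of identifiability, followed by an illustration.

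**1. What two groups can estimate.** Write QoL = a + bM × I(moderate) + bS × I(severe).

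- Moderate only: expected QoL = a + bM.
- Moderate and severe: expected QoL = a + bM + bS.
- Difference: bS. The coefficient on bM is 0.

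The design rows are (1,1,0) and (1,1,1): rank 2 for 3 parameters. Adding a group with neither type, row (1,0,0), gives rank 3, and both bM and bS become estimable. More participants in the two original groups do not change the rank.

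**2. When frequency matters.** The comparison fixes the presence of moderate episodes, not their number. If each moderate episode changes QoL by g, the expected difference between the groups is

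difference = bS + g × (mean moderate count in moderate-plus-severe − mean moderate count in moderate-only).

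This was simulated with 400,000 participants per scenario. All inputs are assumptions: gamma-Poisson moderate counts with mean 4, severe counts with mean 0.3, a severe effect of −5 points and a residual SD of 10.

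| Effect per moderate episode | Contrast, moderate frequency unrelated to severe risk | Contrast, shared frailty | Excess moderate count, shared frailty |
|---|---|---|---|
| 0 | −5.00 | −5.08 | 1.85 |
| −1 | −5.00 | −6.84 | 1.86 |
| −3 | −5.12 | −10.62 | 1.87 |

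The formula agrees: −5 − 1 × 1.86 = −6.86, and −5 − 3 × 1.87 = −10.61. Where the two frequencies are unrelated, the contrast stays near −5 whatever moderate episodes do. Where they share a cause, it moves with the moderate effect but mixes it with the severe one. A result of −10.6 could come from a severe effect of −5 with a moderate effect of −3 per episode, or from a severe effect of −10.6 with none.

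**3. Illustrative rejection rates.** Assume 280 × 0.9 = 252 analysed, 50% to 85% with a moderate episode, 30% of those also with a severe one, effects of 0.5 SD, a yes/no moderate indicator and no clustering.

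- Only severe episodes matter: the stated comparison rejects in 71% to 91% of simulated trials.
- Only moderate episodes matter: it rejects in 5%, the error rate, while moderate-only against none rejects in 78% to 95%.

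The 5% follows from step 1 under that coding. The other figures depend on the assumed prevalences and effect size.

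**4. Recording windows.** Three follow-up windows of 4 weeks give 3 × 4 = 12 weeks of moderate recording in about 104 weeks, against continuous recording for severe episodes. Membership of the moderate-only group thus rests on two different periods of observation.

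**The case against.** The strongest reply is that this is not a fixed analysis. The sentence sits in the endpoint rationale and opens "It will also be possible to assess the effects of both". Section 9 does not list the comparison, and no scale, time point or test is attached to it. The stated response to the NICE point is first of all to record both types of episode. The general psychosocial methods leave room for a regression on episode counts, and the SAP may specify one. The phrase about both effects might also be read as the effect of having both types rather than one, which the comparison does address.

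Much of this stands, and it limits the point to an exploratory statement. It does not remove it. The paragraph names a particular comparison and says what that comparison will deliver, and this is wrong as stated. The alternative reading of the phrase leaves the moderate-episode question, raised a few lines earlier, with no analysis tied to it. The general methods in section 9 are conditional and are not linked to this question.

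Three stronger inferences are tempting, and the document does not support them.

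- *That the trial will yield no information on moderate episodes and quality of life.* Moderate counts are collected at each follow-up visit, and nothing excludes participants without episodes from other quality-of-life analyses.
- *That the comparison holds moderate hypoglycaemia constant, so its effect cancels.* Only presence is fixed. If frequency differs between the groups, the moderate effect confounds the contrast.
- *That the rejection rates above describe this trial.* Their prevalences and effect size are assumed, and they ignore course clustering.

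**Conclusion.** The stated comparison cannot do what is claimed for it. It identifies at best the added association of severe episodes among people who also have moderate ones. The separate contribution of moderate episodes is not identifiable from it at any sample size, and a difference in moderate frequency would bias the severe contrast: by 1.8 to 5.6 points on a true −5 in the assumed shared-frailty scenarios (6.84 − 5 and 10.62 − 5). The rank result needs only the two-group structure in the text. The sizes rest on assumed values.

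The point is worth correcting, but its reach is modest. The comparison is secondary, exploratory and non-randomised. The primary endpoint, the sample size and the randomised comparison of hypoglycaemia rates between arms are untouched.

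**What to change.** Replace the two-group sentence with a single exploratory model, in the protocol or the SAP:

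- Regress quality of life on the moderate episode rate and the severe episode rate as separate terms, in all participants, including those with no episodes of either type.
- Adjust for baseline quality of life and arm, and allow for clustering by course, for example with the GEE approach already planned in section 9.
- State a common time base for the two rates, such as episodes per year. Say that the moderate rate comes from the 4-week windows before visits and the severe rate from recording throughout the trial. Without this the two coefficients cannot be compared.
- To address the cumulative question, compare each coefficient multiplied by the mean rate of its episode type, with confidence intervals.
- Report the results as associations, because episode rates are post-randomisation exposures.

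The cost is one revised sentence and one slightly more complex exploratory model on data already collected. The model does not remove confounding by other patient characteristics, and the moderate rate will be imprecise because it is sampled over short windows. Both limits should be stated with the result.
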